*** * * Background, Purpose, Study Procedures * * ***

Title

EpxCogScreen

Complete Sections 1 - 12. In sections that allow reference to a grant, clearly state section and page numbers. Any information that is different or specific to the local site should be in the SLU application. Specify N/A as appropriate.

1. Background/Rationale

Page numbers from a grant may be referenced in 1a.

- a) **Provide an introduction and background information, including a review of the literature. Describe any past findings leading to the formulation of the study. *?HELP?***

Telemedicine is a modern field of clinical medicine that incorporates telecommunication and information technology to diagnose and managing health care remotely. Interventions range from telephone reminders to remote physician consultation by videoconference. Simple technology such as telephones and SMS texting are ubiquitous forms of communication that have the potential to increase the frequency of physician-patient contact. Such improvements in communication may improve patient adherence, promote education and engagement, allow real-time collection of critical biometric and clinical data over time, and bridge the gap between recognizing adverse events and actual disease management.

One disease that could benefit from earlier detection is dementia. Dementia is characterized by a loss of cognitive functions, such as memory, comprehension, visual-spatial orientation, and judgment. The most common form of dementia is Alzheimer's disease, but vascular dementia and Lewy-body dementia can also cause cognitive impairment. It is estimated that 47.5 million people are affected with dementia worldwide and it is the most common form of disability in the geriatric population over the age of 65, affecting 1 in 9 people in that population [1]. A formal diagnosis for Alzheimer's relies primarily on clinical evaluation by a neurologist and neuropsychometric screens or tests to determine whether cognitive impairment exists.

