Overall Hypothesis: The Epharmix caregiver administered Rapid Cognitive Screen will have statistically significant correlation to the screen administered by a healthcare professional in the clinic.

Aim: Patient- Provider Communication -- To determine if the Epharmix EpxCogScreen can be used to obtain more timely clinical data about cognitive impairment for ongoing physician review, than by traditional methods.

Please save frequently

- c) **Describe the study design (e.g., outline the experimental procedures, describe the ethnographic observation and/or interviewing procedures, or outline survey research methods). Also, indicate if the subjects will be randomized in this study.**

Patients and their caregivers at Saint Louis University Geriatric Clinic will be included in this study and both must consent to participate in the study. The designated caregiver will enroll in the Epharmix program and will receive SMS text messages after one month. The messages will remind the caregiver of when to administer the Rapid Cognitive Screen and give them the option to receive all instructions via text or to use directions from a handout that the caregiver received while in clinic. All patient responses will be recorded through text and all patients will have been previously screened in the geriatric clinic by a health care professional. If the patient has an at-home RCS score decrease of three or more points, the patient's physician will be notified immediately through the Epharmix system and can then contact the patient for follow-up. Subjects will have the ability to opt out of the study electronically via text and phone at any point during the study. The scores of the screen from clinic and home administration will then

Protocol Title: EpxCogScreen

be analyzed to determine if a caregiver administered Rapid Cognitive Screen has high correlation to the screen administered in the clinic. A decrease in the baseline clinic score of three or more points will send an alert to the physician so that they can further evaluate the patient.

The clinic scores will be compared to the at-home RCS scores to determine the correlation coefficient between the two. In addition, at home scores will be compared to clinical diagnoses of dementia obtained from chart review. This will determine the validity of EpxCogScreen use in the geriatric population.

3. Study Procedures

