- a) Does this study involve conduct of research at multiple sites and the SLU PI is the direct recipient of a federal grant for this research? If yes, please complete and attach the Supplemental Application for Coordinating Center Activities. N

Page numbers from a grant may be referenced in 3b and 3c.

- b) Describe all study procedures; from recruitment through end-of-study, that the human subject must undergo in the research project. Please note: The box below is for text only. If you would like to add tables, charts, etc., attach those files in the Attachment section (#12).

Patients will be screened with the Rapid Cognitive Screen (RCS) in clinic as a part of the normal standard of care. Patients and caregivers will receive information about the study and a handout with instructions in the physicians office and can consent if they are interested in participating. If they enroll in the study, the caregiver will receive text message instructions for the RCS one month later. The caregiver can choose to administer the screen with instructions only via text or by using the handout received in the office. He/she will read the instructions to the patient and record responses via text message. The screen will take no more than 15 minutes to complete.

After the data is compiled from the at-home screen, a medical record review will occur. This will look at previously diagnosed medical conditions, which have been indicated in the "Epharmix Data Collection Sheet" in Section 12, and will compare this data to scores received on the RCS screens.

- c) Describe how data analysis will be performed (statistical tests, methods for evaluating data) and indicate the smallest group/unit for which separate reporting will occur. For studies involving a questionnaire, if data and reliability information are available, please describe or provide references. For full board, unfunded studies describe sample size determination and power analysis. If none, please justify.

Data analysis will occur between the patient's at-home and in-clinic RCS scores. The scores will be plotted against one another to determine the correlation between them. The total score correlation, along with the correlation for each individual component of the screen (free recall, clock-drawing, and insight). In addition, the sensitivity and specificity of the at-home screen will be determined based upon clinical diagnoses of patients based on chart review.

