***** Subject Population(h-k) *****

4. Subject Population (continued)

Page numbers from a grant may be referenced in 4h.

- h) Inclusion and Exclusion criteria.

Identify inclusion criteria.

Caregivers over the age of 18 can be recruited, but they must have a patient over the age of 65 in order to be involved in the study. In addition, caregivers must have access to a cell phone and be able to receive and send SMS text messages. Patients in the study must be over the age of 65 in order to participate in the study and must have been previously screened with the

Protocol Title: EpxCogScreen

age of 65 in order to participate in the study and must have been previously screened with the RCS in the clinic. Both patients with and without diagnoses of dementia will be included in the study.

In order to be included in the study, both patients and caregivers must speak English.

Identify exclusion criteria.

Patients under the age of 65 will be excluded from this study.

- i) **Compensation. Explain the amount and schedule of compensation, if any, that will be paid for participation in the study. Include provisions for prorating payment.**

Patients will not receive compensation for their time.

- j) **Describe who will cover study related costs. Explain any costs that will be charged to the subject.**

Epharmix has direct contracts with Verizon, T-mobile, Boost, Sprint, and AT&T so that no costs are transmitted to participants with these service providers. Other service providers may result in charges depending on the individual plan.

Epharmix will also be covering the cost of postage stamps for the patient and caregiver to send in their consent forms.

- k) **Estimate the probable duration of the entire study, including data analysis and publication. In addition, estimate the total participant duration.**

The study will take approximately 18 months for the recruitment of patients, data collection and analysis, and publication. The total duration of patient participation in the study will be one month from the date of enrollment.

* * * Risks * * *

5. Risks

There is no research that can be considered totally risk free (e.g., a potential risk of breach of confidentiality). Therefore, when describing the risk, the lowest level of risk is "no more than minimal risk."

- a) **Describe any physical, psychological, social, legal or other risks.**

Possible risks include a breach of confidentiality of PHI and annoyance due to repetition of messages.

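### Section 3c scores the home RCS against chart diagnoses that an earlier clinic RCS may have prompted, so sensitivity may be overstated; the net direction for specificity is uncertain

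*Protocol*

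**What the plan says.** Section 3c: "the sensitivity and specificity of the at-home screen will be determined based upon clinical diagnoses of patients based on chart review". Section 2c names the target condition: "at home scores will be compared to clinical diagnoses of dementia obtained from chart review". It presents the score correlation and this comparison together as what will settle whether the tool is valid in older patients.

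On prior exposure to the same instrument, section 3b says "Patients will be screened with the Rapid Cognitive Screen (RCS) in clinic as a part of the normal standard of care". Section 2c says "all patients will have been previously screened in the geriatric clinic by a health care professional", and section 4h requires that patients "must have been previously screened with the RCS in the clinic".

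On the chart review, section 3b says "After the data is compiled from the at-home screen, a medical record review will occur" and "This will look at previously diagnosed medical conditions". Neither section distinguishes diagnoses by whether they came before or after the clinic RCS, or by how they were reached.

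On how dementia is diagnosed, section 1a says that a formal Alzheimer's diagnosis "relies primarily on clinical evaluation by a neurologist and neuropsychometric screens or tests to determine whether cognitive impairment exists". The same section also says that screens raise awareness and are not themselves diagnostic, and that a formal diagnosis needs a physical examination, neurological and psychiatric evaluation and laboratory tests.

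**The concern.** Sensitivity and specificity mean what they appear to mean only if the reference label is assigned independently of the test. Here the test is the RCS given at home by a caregiver, and the label is a routine diagnosis in patients who all had the RCS in clinic. If a low clinic score starts the work-up that ends in a charted diagnosis, the diagnosed group is enriched for patients whose dementia shows on the RCS. Those patients are also more likely to score low on the same items at home about a month later. Dementia patients whom the RCS tends to miss are less likely to reach the diagnosed group, so the home screen's misses are under-counted.

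A thorough work-up does not remove this, because the bias lies in who is selected for work-up and not in how well it is done. At stake is whether the sensitivity from 3c can be read as the sensitivity of home screening for dementia.

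**Working it through.** The protocol states no expected home sensitivity or specificity, so there is no figure of its own to reproduce. The calculation below shows direction and rough size only.

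**Inputs**
- Clinic RCS sensitivity for dementia, s_c = 0.89 (section 1a). The value 0.80 is added as an assumption.
- True home sensitivity, s_h = 0.75 (assumption).
- Correlation of home and clinic results among dementia patients, φ = 0.2, 0.4, 0.6 (assumption). With s_h = 0.75 and s_c = 0.89 the largest attainable φ is (0.75 − 0.75×0.89)/√(0.75×0.25×0.89×0.11) = 0.0825/0.1355 = 0.609.
- Home specificity 0.94 (the section 1a figure for the RCS, assumed to carry over to the home).
- Dementia prevalence in the sample, p = 0.30 (assumption).

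**Sensitivity.** Suppose every charted diagnosis is true dementia that followed a positive clinic RCS. Measured sensitivity is then

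P(home+ | clinic+, dementia) = s_h + φ·√(s_h(1−s_h)·s_c(1−s_c)) / s_c.

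For s_c = 0.89 the second term is φ × 0.1355/0.89 = 0.152φ. For s_c = 0.80 it is φ × 0.1732/0.80 = 0.217φ.

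| s_c | φ = 0.2 | φ = 0.4 | φ = 0.6 |
|---|---|---|---|
| 0.89 | 0.780 | 0.811 | 0.841 |
| 0.80 | 0.793 | 0.837 | 0.880 |

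Against a true 0.75, the excess is 3 to 9 points at the cited 0.89. If only half the diagnoses followed a positive RCS and the rest were unrelated to it, these values average with 0.75. That gives 0.765 to 0.796 at s_c = 0.89 (1.5 to about 4.5 points) and 0.772 to 0.815 at s_c = 0.80.

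The direction does not depend on choosing 0.75. If home and clinic sensitivity are both 0.89, the formula reduces to 0.89 + φ(1 − 0.89), which is 0.923 at φ = 0.3 and 0.956 at φ = 0.6.

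**Specificity, same model.** The undiagnosed group is everyone without dementia plus the dementia patients who passed the clinic RCS:

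Sp = [(1−p)·0.94 + p·((1−s_h)(1−s_c) + φ·√(s_h(1−s_h)s_c(1−s_c)))] / [(1−p) + p(1−s_c)].

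For s_c = 0.89 and φ = 0.2: (0.658 + 0.30×0.0546)/0.733 = 0.920.

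| s_c | φ = 0.2 | φ = 0.4 | φ = 0.6 |
|---|---|---|---|
| 0.89 | 0.920 | 0.931 | 0.942 |
| 0.80 | 0.899 | 0.913 | 0.927 |

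Specificity falls below 0.94 in five of the six cells. It rises only where a dementia patient who passed in clinic passes at home more than 94% of the time. At s_c = 0.89 and φ = 0.6 that probability is 0.1088/0.11 = 0.989; at φ = 0.4 it is 0.0817/0.11 = 0.743.

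**With more under-diagnosis.** Section 1a puts undiagnosed Alzheimer's disease at 29 to 76%. Take home and clinic sensitivity as 0.89, p = 0.30 and diagnosis only after a positive clinic RCS. As φ goes from 0 to 0.9, specificity runs from 0.848 to 0.875 at 29% undiagnosed and from 0.736 to 0.744 at 76%. With the undiagnosed share held fixed, dependence on the RCS raises specificity a little, but missed cases pull the net value well below 0.94.

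**The case against.** The strongest reply is that the causal route is not documented. Section 1a says screens do not diagnose and describes a full evaluation before any formal diagnosis. No section says that charted diagnoses followed an RCS or were first made in this clinic. Section 11 marks physician or clinic records as the medical-record source, but that does not show where a diagnosis originated. Patients with an existing dementia diagnosis are eligible, and some diagnoses may predate any RCS. The home test is also a separate administration by a different person.

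Much of this stands. It rules out the inference that the reference is itself an RCS result: on the protocol's own account the RCS could at most prompt a diagnosis, not make it. The share prompted is unknown and could be small. A separate administration does not remove the bias, however, because the study's own hypothesis is that home and clinic scores correlate.

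Two other stronger readings also fail. A reader might infer that specificity is inflated along with sensitivity; the working shows it falls in most cells. A reader might also take the largest figure, 13 points (0.880 against 0.75), as the size of the problem. It needs an assumed clinic sensitivity of 0.80, the highest correlation used and every diagnosis following a positive RCS.

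Finally, accuracy is not the stated hypothesis, which concerns correlation, and the choice of subsets can be left to an analysis plan. That is fair, but the chart review is set out in the protocol, and no later plan can stratify on dates and bases that were not abstracted without returning to the charts.

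**Conclusion.** The point holds as a risk that the protocol leaves open, not as a demonstrated bias. The reference in 3c is not secured as independent of the RCS. To the extent the clinic RCS prompted diagnoses, and home and clinic results are correlated among dementia patients, sensitivity is overstated. The excess is 3 to 9 points at the cited clinic sensitivity of 0.89 if all diagnoses followed a positive RCS, and about half that if half did. These figures rest on an assumed true home sensitivity of 0.75 and correlations of 0.2 to 0.6. The net direction for specificity is uncertain.

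The bias may be smaller than sampling error. With an assumed 30 diagnosed among the 100 patients, the 95% half-width at 0.75 is 1.96×√(0.75×0.25/30) = 0.155. Unlike sampling error, though, it would not shrink with more patients and would not show in the interval. It is worth correcting because it changes what the accuracy result can support.

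**What to change.** **Chart review (3b and the data collection sheet).** For each dementia diagnosis record its date, its basis (full geriatric or neurological evaluation, or screen only) and the date of the first clinic RCS. The sheet is an attachment that is not shown, so add only the fields it lacks.

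**Analysis (3c).** Add a short paragraph:
- Report sensitivity for all charted dementia diagnoses. Beside it, report sensitivity separately for diagnoses that predate or were made without the RCS, and for those that followed it, with intervals.
- State that the all-diagnoses figure is not independent of the RCS.
- State that specificity may be biased in either direction, because undiagnosed patients were partly sorted by the clinic RCS and include missed cases.

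**Cost.** Up to three more fields in a review already planned, and one paragraph. The strata will be small: with an assumed 15 diagnosed patients in one, the half-width at 0.75 is 1.96×√(0.75×0.25/15) = 0.22. Diagnoses that predate the RCS may also be longer-standing, more advanced cases, which can itself raise sensitivity. For both reasons show the strata side by side and do not make the restricted figure the headline.

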***** Subject Population(a-g) *****

4. Subject Population - In the space below, please detail the participants that you are requesting to recruit (include description of each group requested).

a) Number of evaluable subjects to be accrued.

200 (100 patients and 100 caregivers)

Exceeding the number listed here is a protocol violation. Prior IRB approval is required if additional participants are to be accrued. If applicable, this number should be consistent with your power analysis described in 3b.

b) What is the expected age range of subjects? (For example: ≥ 18 yrs to 90 yrs).

Patients must be over the age of 65 to participate. Caregivers can be greater than 18 years old to 90.
--

c) Requested Participant Description (e.g., gender, ethnicity, socio economic status, etc.). Include description of each group requested.

The population used will include all genders, socioeconomic, and ethnic backgrounds. Both patients with and without diagnoses of dementia will be included in the study.
--

d) If including vulnerable populations (minors, pregnant women and fetuses, <a href=<https://www.slu.edu/Documents/research/IRB/Neonates.docx> target=_blank>neonates, non-English speaking, economically or educationally disadvantaged, prisoners, adults temporarily or permanently unable to consent for themselves): 1) provide the rationale for the importance of including this population in the research, and 2) specify the measures being taken to minimize risks to potentially vulnerable subjects. Click on hyperlinks to access <a href=<https://www.slu.edu/division-of-research-administration-home/institutional-review-board->

Protocol Title: EpxCogScreen

(irb)/general-guidelines target=_blank>SLU Guidelines containing additional considerations and strategies for mitigating risks.

Any patient that visits the geriatric clinic at SLU and is over the age of 65 is eligible to participate in the study. Cognitive impairment and dementia are prevalent in this population, and early diagnosis is important to allow for patients to plan for their futures and have early intervention in the disease. Screening tools are used for early diagnosis, and this study would determine if an at home dementia screen could be used in the general geriatric population for earlier detection of disease.

Patients will be informed of the risks before the study, and all patients have the right to accept or decline participation in the study. However, if the patient has an appointed proxy, the proxy will be informed of the risks and will then make a decision of participation for the patient.

- e) **If women, minorities, or minors are not included, a clear compelling rationale must be provided unless not applicable. If federally funded reference appropriate section of the grant.**

N/A

- f) **If any subjects are students or employees, specify the measures being taken to minimize the risks and the chance of harm to these potentially vulnerable subjects. See SLU Guidelines for additional considerations and strategies for mitigating risks.**

- g) **How will potential participants be recruited (e.g., flyer, e-mail, web posting, telephone, etc.)? Upload recruitment materials in the Attachment Section (#12). Important to remember: potential subjects cannot be contacted before IRB approval.**

Recruitment will occur at the Saint Louis University Geriatric Clinic waiting room as part of the check-in process. The handout that will be used is attached to Section 12 and is titled "EpxCogScreen Recruitment Flyer - Version 2." If both the patient and caregiver are interested in participating, they may both choose to be consented in the clinic and then enrolled in the program by a study member. If they wish to be consented at a later time, a study member will call the caregiver and patient to provide information and enroll them in the study.

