Even if participants receive information about the study over the phone, consent will be documented by patient and caregiver signature on the consent forms sent via mail. The participants will sign two copies of the consent form, one to keep for personal reference, and another one which will be mailed to [name] office using pre-addressed and stamped envelopes provided with the consent forms. The envelopes will be provided by the SLU Geriatric Clinic and postage costs will be covered by Epharmix.

Subjects will be informed that these communication lines are unsecured and may be non-confidential. They will have the opportunity to ask questions directly and consent or decline to participate. After enrollment, subjects will then be sent an initial message with information about the trial electronically according to their registered phone number, including the ability to opt -out at any point. Standard data and messaging charges may apply.

Protocol Title: EpxCogScreen

- 2) If the study involves adults unable to consent for themselves (whether diminished capacity to consent is temporary, permanent, progressive or fluctuating), please address the following: a) how is capacity to provide consent being assessed (initially and throughout study, if applicable); b) if unable to provide consent, how is LAR being determined (See SLU LAR Guidelines); c) if unable to provide consent, will assent be obtained and if not, why not?; d) if unable to provide assent, will dissent be honored and if not, why not? Note: participants initially unable to provide consent for themselves are expected to be given an opportunity to provide consent once capacity is gained. See SLU Guidelines for Adults Unable to Provide Consent for additional detail.

All patients and caregivers will be consented, unless they have a legally authorized representative (LAR) who will provide consent for him/her. A patient will also not be able to provide consent if a qualified practitioner's documents that the patient lacks decision-making capacity or if an individual has been ruled incompetent by a court of law. However, if neither of these apply, the patient's understanding of the research will be assessed through three true/false questions. These questions are attached in section 12.

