b) If it is determined that the participant is unable to consent, an LAR may sign the consent form for the patient. LAR guidelines and documentation for the use of a LAR are attached. The LAR will be chosen in the following order:

- a.[Attorney in Fact/Power of Attorney]
- b.Spouse, unless the patient has no spouse, or is separated, or the spouse is physically or mentally incapable of giving consent, or the spouse's whereabouts is unknown or the spouse is overseas;
- c.Adult child;
- d.Parent;
- e.Brother or sister;
- f.Relative by blood or marriage.

c, d) Both assent and dissent will be honored and obtained verbally. The attached assent script and form will be used in cases where the participant does not have consenting capacity.

Note: Any assent documents which will be used per the Adults Unable to Provide Consent guidance, should be appropriately named and uploaded using the Add button and the Consent drop down menu selection.

Informed Consent

Title	Consent Type	Attached Date
Approved_Assent Script and Form Version 2	Consent	04/10/2018
Approved_Consent Form- Version 6	Consent	04/10/2018

Title	Approved_Assent Script and Form Version 2
Consent Type	Consent
Upload Consent Document	X Attachment Approved_Assent Script_2

Protocol Title: EpxCogScreen

Upload your informed consent document. Use the SLU Informed Consent Template to create your consent document. If more than one consent will be used (e.g., adult consent, parental consent, etc.), label the consent documents with these headings to help distinguish them from one another.

Upload any assent documents which will be used for adults who are unable to provide consent here and not in the assent section.

Title	Approved_Consent Form- Version 6
Consent Type	Consent
Upload Consent Document	X Attachment Approved_consent version 6

Upload your informed consent document. Use the SLU Informed Consent Template to create your consent document. If more than one consent will be used (e.g., adult consent, parental consent, etc.), label the consent documents with these headings to help distinguish them from one another.

Upload any assent documents which will be used for adults who are unable to provide consent here and not in the assent section.

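### Section 4d and the opening of section 9 item 2 let a proxy decide study entry because one exists; item 2b requires a finding of incapacity, and sections 2c and 9 item 1 require the patient's own consent

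*Protocol*

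**What the plan says.** Five places in the protocol bear on who decides.

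- **Section 2c (study design)** says of patients and caregivers that "both must consent to participate in the study". It states no exception.
- **Section 4d (vulnerable populations)** first says that "all patients have the right to accept or decline participation in the study". The next sentence makes an exception: "if the patient has an appointed proxy, the proxy will be informed of the risks and will then make a decision of participation". The only condition is that a proxy has been appointed.
- **Section 9 item 1** repeats that both parties need to consent, again with no exception. For those who consent later, it says that capacity is assessed with three true/false questions.
- **Section 9 item 2, opening of the answer**, says: "All patients and caregivers will be consented, unless they have a legally authorized representative (LAR) who will provide consent for him/her". It continues: "A patient will also not be able to provide consent if a qualified practitioner's documents that the patient lacks decision-making capacity", and adds a court ruling of incompetence. If neither condition applies, understanding is assessed with the three questions.
- **Section 9 item 2b** says: "If it is determined that the participant is unable to consent, an LAR may sign the consent form for the patient". The order of LARs that follows begins with an attorney in fact or power of attorney.

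On assent, the answer to item 2c and 2d says that assent and dissent are obtained verbally and honored. It then says: "The attached assent script and form will be used in cases where the participant does not have consenting capacity".

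**The concern.** Two different triggers are written into the protocol. In section 4d and the opening of section 9 item 2, the trigger is that a representative exists. In item 2b it is that the patient cannot consent. The two give opposite answers for a patient who has capacity and has also named a proxy.

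Such patients are to be expected. Sections 4c and 4h deliberately include patients without a dementia diagnosis, all over 65, from a geriatric clinic. Participation sends the patient's name, phone number and text responses to an outside company (section 7d) and leads to a medical record review (section 3b). Recruitment takes place at clinic check-in (section 4g), where a team member could follow section 4d in good faith and take the proxy's decision in place of the patient's.

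**Working it through.** No arithmetic applies, and the protocol gives no figure to reproduce. The check applies each rule as written to three kinds of patient and records who must decide on entry.

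| Rule | Capacity, no proxy | Capacity, proxy appointed | No capacity, appointed LAR |
|---|---|---|---|
| Section 2c | Patient | Patient | Patient, so entry is barred |
| Section 4d | Patient | **Proxy** | Proxy |
| Section 9 item 1 | Patient | Patient | Patient, so entry is barred |
| Section 9 item 2, opening | Patient | **LAR** | LAR |
| Section 9 item 2b | Patient | Patient | LAR |

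1. **First column.** All five rules agree.

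2. **Second column.** Section 4d and the opening of item 2 give the decision to the representative. The other three leave it with the patient.

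3. **Third column.** Sections 2c and 9 item 1, taken literally, exclude the very patients whom item 2b provides for. These two sections therefore cannot be the governing rule as they stand, and cannot be used to settle the second column.

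4. **Could having an LAR simply mean lacking capacity?** The text points the other way. After the LAR clause, item 2 says that a patient will *also* be unable to consent if incapacity is documented, which makes incapacity an additional ground. A power of attorney, first in the LAR order, does not by itself show incapacity.

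5. **What is obtained from the patient in the second column under section 4d?**
   - Consent to entry: not required, because the proxy decides.
   - Assent script and form: not applicable, because they are limited to participants without consenting capacity.
   - Three questions: unclear. In item 2, the phrase about neither condition applying may cover only documented incapacity and a court ruling, in which case the patient is still asked. Item 1 states the check without an LAR exception, but only for later consent. In either case it tests understanding or capacity and is not a decision to take part.
   - Verbal agreement to exchange health information by text: required by section 5b, with no proxy exception. It covers the communication channel, not entry or chart review.

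**The case against.** The strongest defense is context. The form prompts for section 4d and section 9 item 2 ask about adults who cannot consent for themselves, so both proxy sentences can be read as answers about those adults only. The LAR order also reaches spouses, adult children, siblings and other relatives. If merely having such a person displaced the patient, very few patients would consent for themselves, which cannot be intended. Item 2b then supplies the specific rule for the general sentence. The LAR guidelines, assent script and consent form are attachments not shown here, and may define when an LAR acts.

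This shows what was probably intended. It does not remove the conflict. The section 4d prompt covers vulnerable groups in general, and the answer there opens with any clinic patient over 65. The proxy sentence is then set as an exception to the right of all patients, with no mention of capacity. The wording that separates having an LAR from incapacity in item 2 also remains.

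A reader might go further and infer that a capable patient with a proxy would be enrolled with neither consent nor assent of any kind. The documents do not support that. Section 5b requires the patient's own verbal agreement on texting health information. Sections 2c and 9 item 1 require the patient's consent. The statement that assent and dissent are honored carries no limit in its own wording; only the script and form do. Section 5b also lets patients opt out through their physician or the research team.

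**Conclusion.** The point holds as a contradiction about who decides on study entry. Section 4d and the opening of section 9 item 2, followed literally, replace the decision of a patient who has capacity. Item 2b and sections 2c and 9 item 1 say otherwise. This is what the wording permits, not a stated intention.

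Its size cannot be derived. A count among the 100 planned patients would need the share with a proxy, the share of those with capacity, and how often staff would follow section 4d over the other sections. The protocol gives none of these. A reader might also infer that data would have to be withdrawn; nothing in the protocol says so. No endpoint, analysis or sample size is shown to be affected. The conclusion assumes that the attachments not shown do not already settle the trigger; even if they do, the protocol text should agree with them. The change is worth making because the document that staff follow should give one answer on who consents.

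**What to change.** Reconcile sections 2c, 4d, 9 item 1 and 9 item 2 so that one condition governs throughout:

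- **Sections 4d and 9 item 2 (opening):** the patient decides. A proxy or LAR decides only if lack of capacity has been documented by a qualified practitioner, ruled by a court, or found through the existing three questions. In those cases the patient's assent is obtained and dissent honored, as the answer to item 2c and 2d already provides.
- **Section 9 items 1 and 2:** put the three questions to every patient without documented incapacity or a court ruling, including patients who have a proxy, whether they consent in clinic or later. Say explicitly which conditions exempt a patient from them.
- **Sections 2c and 9 item 1:** add the exception that, for a patient lacking capacity, the LAR consents with the patient's assent.

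The cost is a wording amendment, plus the three questions for some additional patients. The procedures used are already in the protocol. The attached LAR guidelines, consent form and assent script should be checked for agreement at the same time.
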